- **I phase (only retrospective phase)** → it will cover all patients underwent to either medical treatment or surgery for which all data are available, with a follow up of 5 years at March 31, 2023. We will retrieve all patients data from January 1994 till March 31, 2018. At the end of “phase I”, we foresee an “ad interim” analysis.
- **II phase (ambispective)** → we will further include all patients retrieved from the archives between April 1, 2018 and the April 30, 2023, as well as all prospectively enrolled patients till December 31 2023, so that the last patient enrolled will end the 5-years follow-up phase within December 31, 2028.

Inclusion criteria

- Age >18 years old;
- Presence of BCLM;
- BCLM and extra-hepatic disease;
- Any treatment;
- Ability to understand and sign the informed consent.

Exclusion criteria

- Inability to provide the informed consent;
- Patients who underwent Best Supportive Care or palliation.

Variables and procedures

The following data will be retrieved from medical archives of each participating center for all retrospectively enrolled patient.

Prospectively enrolled patients' data will instead be collected in the related medical record and reported, alongside all other patients' data, in an electronic dataset protected by password and accessible only to the PI and the co-investigators, and to any other person authorized by PI.

In depth, the following data will be included:

- Anonymized ID;
- Demographic and anthropometric data (e.g., age, sex, BMI, etc..);
- Name of the participating center;
- ER, PR and HER2 status,
- Presence of BRCA1-2 mutation,
- Neoadjuvant-radiotherapy,
- Neoadjuvant endocrine therapy,
- Neoadjuvant-chemotherapy,
- Neoadjuvant-anti-HER2,
- Date of breast surgery,
- Breast tumor T and N,
- Adjuvant radiotherapy,

- Ad-endocrine therapy, Ad-chemotherapy, and Ad-anti-HER2,
- Date of liver metastasis diagnosis,
- Date of liver surgery,
- Liver surgery,
- Liver resection major/minor (Segmental or wedge resection or Left Lateral),
- R status,
- Number of liver metastasis,
- Size of the bigger lesion (mm),
- Distribution (uni or bilobar),
- Postoperative morbidity,
- Hormone receptor expression in the liver metastasis (ER+, PR+),
- Extra-hepatic disease,
- Site of Extra-hepatic disease,
- Mortality and cause;
- Date of death or last FU observation,
- Recurrences,
- Site of recurrences,
- Date of recurrences.

ENDPOINTS

Primary endpoint

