The primary endpoint is to analyze the efficacy of liver surgery as compared to medical therapy alone in terms of 5-years overall survival in patients with breast cancer who underwent to liver resection or medical therapy alone.

Secondary endpoints

- Recurrence rate;
- Post-operative mortality (in patients who underwent to surgical treatment).
- Post-operative complication (in patients who underwent to surgical treatment).
- To assess potential predictive factors of 5-years overall survival in patients with breast cancer who underwent to either liver resection or medical therapy alone.
- To assess recurrence free survival (RFS) of liver surgery as compared to medical therapy alone in terms of 5-years overall survival in patients with breast cancer who underwent to liver resection or medical therapy alone.
- To assess potential predictive factors of 5-years RFS in patients with breast cancer who underwent to either liver resection or medical therapy alone.

STATISTICAL ANALYSIS PLAN

Sample size calculation

The sample size was computed based on the assessment of an improvement in the OS of patients surgically treated as compared to systemic therapy alone.

Based on the evidence from Ruiz and colleagues [10], which reported a 5-years OS of 24% among women treated only with medical therapy and of 69% among those surgically treated, we hypothesize to obtain in our study sample an OS of 60% in the treated group and of 25% in the systemic therapy group.

As such, considering a treatment/control ratio of 0.15/0.85, a two-sided log-rank test with an overall sample size of 117 subjects (99 in the systemic therapy group and 18 in the surgical treatment group) achieves 90% power at a 0,05 significance level to detect a hazard ratio of 0,37 when the proportion of 5-year OS in the control group is 25%. The study will consider a time-window of 30 years of total enrolment (from 1994 to 2023) and a follow-up period of 5 years, for a total time of 35 years. The accrual pattern across time periods is uniform (all periods equal). We expect no subjects drop out both in the control group and treatment groups. The expect no. of events is of 96,5 in the control group and 14,3 in the treatment group. The sample size calculation was performed with PASS2022 v22.0.3 [12,13]. Such sample size estimation is consistent with the disease specific metastasis prevalence and on the no. of involved centers. In fact, we overall expect to include in both retrospective and

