prospective phase 75-80 patients/center, for overall sample of 675-720 patients. Particularly, the retrospective phase, which will include patients till 2017 will consist of about 500 patients, already consistent with the sample size estimate provided, whilst the other will pertain to the period 2018-2023.

Statistical analysis

The sample will be described in its clinical and demographic characteristics by descriptive statistics techniques. In depth, qualitative data will be expressed as absolute and relative percentage frequency, whilst quantitative variables either by mean and standard deviation (SD) or median and interquartile range (IQR), as appropriate. To verify the Gaussian distribution of quantitative variables, the Shapiro-Wilk test will be applied.

Missing values, as <5% in all cases, were treated by *imputeR* package, using multiple imputation with Lasso Regression methods centered on the mean as for quantitative data, whilst classification trees for imputation by “rpartC” function, centered on the mode, i.e. most represented class object, were applied on qualitative data [14].

Between groups differences were analyzed by either the Chi squared test or the Fisher-Freeman-Halton test for qualitative data, whilst either the Student’s t test or non-parametric Mann-Withney U test will be applied on quantitative data, as appropriate.

Differences between groups will be further exemplified by clustered violin plots or plots describing pre-post variation in individual groups. Such plots will be produced with the R packages “ggplot2”, “ggstatsplot”, “ggpubr”, “ggprism”, and “ggsignif” [15-19].

OS will be calculated from the date of treatment initiation through the date of death from any cause; subjects alive at the last follow-up will be censored. Overall survival and RFS probabilities at 5 years will be estimated using the Kaplan Meier method and compared by the log-rank test. The KM curve will also be reported. The analysis will be performed with the R package “*ggplot2*” and “*survminer*” R packages [15,20].

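### Overall survival starts at treatment initiation, a date not collected for medical patients and undefined for resected patients, and time before surgery is not handled, so the primary contrast can be biased.

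*Protocol*

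**What the plan says.** All places are in the Protocol.

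- **Statistical analysis, origin:** "OS will be calculated from the date of treatment initiation through the date of death from any cause". Patients alive at last follow-up are censored.
- **Statistical analysis, comparison:** "Overall survival and RFS probabilities at 5 years will be estimated using the Kaplan Meier method and compared by the log-rank test". Cox models follow for prognostic factors, with weighted Cox regression if proportionality is doubtful. There is no landmark, time-dependent exposure or delayed entry.
- **Primary endpoint:** the groups are "patients with breast cancer who underwent to liver resection or medical therapy alone", that is, defined by treatment actually received.
- **Variables and procedures:** the dates listed are breast surgery, "Date of liver metastasis diagnosis", "Date of liver surgery", recurrences, and death or last observation. Medical therapy appears only as undated neoadjuvant and adjuvant items, for example "Ad-endocrine therapy, Ad-chemotherapy, and Ad-anti-HER2".
- **Sample size calculation:** it assumes "an OS of 60% in the treated group and of 25% in the systemic therapy group", a 0.15/0.85 split and 675-720 patients expected.

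**The concern.** The origin of the primary endpoint and the data list do not fit together. At the planned split the medical group is 0.85 × 675 = 574 to 0.85 × 720 = 612 patients, and none of them has a listed date from which OS could be counted as defined.

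For resected patients the term is open. Calling the surgical arm the treated group suggests the date of operation. But the inclusion criteria admit any treatment, so systemic therapy before resection is not excluded. Two readings follow:

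- **(a) Common early origin.** Both groups start at diagnosis or first therapy. Resected patients cannot die before their operation, and surgical candidates who die waiting count as medical. This is immortal time.
- **(b) Surgery timed from the operation.** Medical patients start at diagnosis or first therapy and resected patients start later, so the groups enter at different points of the disease.

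Two analysts could both follow the text and obtain primary results that differ in size and even in direction. The ad interim analysis after phase I inherits the problem. Weighted Cox regression addresses non-proportional hazards, not person-time assigned to the wrong group.

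**Working it through.** **The plan's own figures.** HR = ln 0.60 / ln 0.25 = 0.368 (stated 0.37). With exponential survival, 30 years of uniform accrual and 5 years of follow-up, expected events at 99.45 and 17.55 patients are 96.46 and 14.27 (stated 96.5 and 14.3). Lakatos power at 117 patients is 91.9% with yearly steps and 93.3% with fine steps (stated 90%). The sizing is therefore reproduced, rests on a constant hazard, and does not involve the time origin.

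**Hand check, no effect of surgery.** Inputs from the Protocol: 25% 5-year OS and 15% resected. Assumed: a fixed lag of 6 months and a constant hazard. Follow-up is cut at 5 years. The hazard is −ln 0.25 / 5 = 0.2773 per year.

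- Whole cohort, per patient: 0.75 deaths and 0.75 / 0.2773 = 2.705 years.
- Per resected patient, counted from the early origin: 1 − 0.25^0.9 = 0.7128 deaths and 0.5 + 0.7128 / 0.2773 = 3.071 years, a rate of 0.2321.
- Remaining (medical) patients: 0.75 − 0.15 × 0.7128 = 0.6431 deaths and 2.705 − 0.15 × 3.071 = 2.244 years, a rate of 0.2865.
- Reading (a): 0.2321 / 0.2865 = **0.81**.
- Reading (b): resected patients have the rate 0.2773 after surgery, and 0.2773 / 0.2865 = **0.97**.
- Time split at surgery: medical years become 2.244 + 0.15 × 0.5 = 2.319, a rate of 0.6431 / 2.319 = 0.2773, equal to the rate after surgery, so the ratio is **1.00**.

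**Simulation, true HR 1.** The 5-year OS, resected share and 5-year cut are as above. Assumed, because the Protocol gives neither: a lognormal lag (sigma 0.5) with median 1, 3, 6 or 12 months, and the hazard shape. Candidates are drawn at random. HRs come from 1,500,000 patients per scenario, and two-sided false-positive rates from 2,000 samples of 700.

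| Reading | Hazard | HR at 1 / 3 / 6 / 12 months | False positives |
|---|---|---|---|
| (a) | constant | 0.96 / 0.89 / 0.80 / 0.65 | 6 / 15 / 46 / 96% |
| (a) | gamma frailty, variance 1 | 0.92 / 0.80 / 0.67 / 0.50 | – |
| (a) | rising (Weibull 1.5) | 0.99 / 0.97 / 0.91 / 0.80 | 5 / 6 / 9 / 40% |
| (b) | constant | 0.99 / 0.98 / 0.97 / 0.94 | 6 / 5 / 6 / 8% |
| (b) | gamma frailty, variance 1 | 0.95 / 0.88 / 0.79 / 0.67 | 6 / 15 / 46 / 89% |
| (b) | rising (Weibull 1.5) | 1.03 / 1.09 / 1.15 / 1.26 | 6 / 12 / 24 / 51% |

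In the last row the false positives are against surgery. With resection as a time-dependent exposure from diagnosis, the HR is 0.994-1.006 and false positives are 4.5-6.2% in all 20 scenarios (these three shapes plus frailty variance 0.5 and Weibull 1.25).

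**Selection is a separate matter.** With a constant hazard and a 6-month lag, candidates whose hazard is 20% or 40% lower for reasons unrelated to surgery still give a time-dependent HR of 0.80 or 0.60.

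**The case against.** **A separate SAP could supply the handling of pre-surgery time, and a case report form could hold therapy start dates.** Either is possible. But the Protocol itself fixes the origin, the variable list and the test, and these three do not fit together.

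**The size of the bias is assumed.** This stands. The Protocol gives no lag to surgery, and its sizing implies a constant hazard. Under that hazard, reading (b), which is closer to the text, gives only 0.94-0.99 with false positives of 5-8%. At a 1-month lag every tabulated false-positive rate is 5-6%. The largest distortions need reading (a) or frailty together with long lags. That limits what can be said about size, but it does not settle which origin applies.

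**Adding one date and defining the term would be enough.** That would make the origin computable. It would leave either the immortal time of (a) or the unequal starting points of (b).

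**A time-dependent HR does not give the two 5-year percentages the endpoint suggests.** This stands as a cost. A landmark comparison from a common origin also removes immortal time and gives curves, but these are conditional on reaching the landmark.

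**Archived patients referred after diagnosis also enter late.** True, and no referral date is listed. If all resected patients entered at surgery and this were ignored, the null time-dependent HR would be 1.00-1.05, a small shift.

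**Conclusion.** The concern holds. As written, the OS origin cannot be computed from the listed data for the medical group and is undefined for the surgical group, and neither reading gives a fair comparison by log-rank. With no true effect, reading (a) gave HRs of 0.50 to 0.99, toward surgery. Reading (b) gave 0.67 to 1.26: slightly toward surgery with a constant hazard, clearly so with heterogeneous patients, and against surgery with a rising hazard.

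These sizes rest on assumed lags and hazard shapes and may be negligible if surgery follows quickly. None reaches 0.37, so this bias alone would not produce the planned effect in the scenarios tested. A larger sample only makes the test more certain of a biased value. Because it concerns the time origin of the primary endpoint in a non-randomised comparison, it must be settled before any outcome analysis, including the ad interim one.

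**What to change.** 1. Start OS at the date of liver metastasis diagnosis for every patient.
2. Make the primary comparison a Cox model with resection as a time-dependent exposure: medical until the date of liver surgery, surgical afterwards. Adjust for pre-specified listed covariates, for example number, size and distribution of metastases, extra-hepatic disease, ER/PR/HER2, age and center. Use the same rule in the ad interim analysis.
3. For patients enrolled prospectively after diagnosis, record the enrolment date and use delayed entry.
4. Optionally show landmark curves, labelled as conditional on reaching the landmark.
5. If treatment initiation is kept for any analysis, define it for resected patients and add the start date of medical therapy to the list.
6. State that confounding from the selection of surgical candidates remains. The RFS origin is not part of this change.

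**Cost.** The two key dates are already listed, and enrolment is the one new date. Archives close on April 30, 2023 and the plan includes "all prospectively enrolled patients till December 31 2023", so about 8 months are prospective. With even accrual that is 8/360 of 675-720 = 15-16 patients, or 8/72 of the 175-220 beyond the first 500 = 19-24. At these shares the null time-dependent HR was 0.995-1.004 with or without delayed entry.

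Simulated power of the time-dependent model at HR 0.37 is above 99% at 500 and at 675-720 patients. At 117 it is 77% to 68% for lags of 1 to 12 months, against about 81% for a plain log-rank with the same 5-year cut. The sample-size paragraph therefore needs a matching sentence, and the 90% statement should not be carried over. If the present analysis would have followed (a), the estimated benefit will probably be smaller. A landmark curve is a different quantity from 5-year OS: with a constant hazard, medical survival from month 12 to year 5 is 0.25^0.8 = 33%, not 25%.

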The primary treatment for BCLM remains chemo-therapy and, more recently, targeted immunotherapy. Liver metastases from other primary tumors, such as colorectal cancers, are routinely resected as part of standard management. Breast cancer rarely develops isolated liver metastases because neo-plastic cells at this stage have often already reached systemic circulation with the possibility of further localization, unlike colon cancer, where the liver, through the portal system, is the first organ to be colonized. Therefore, the role of liver resection in BCLM remains controversial [6-8].

Hepatic resection and/or ablation was not associated with a survival advantage in some studies [9], whilst in other disclosed a remarkable improvement as compared to systemic treatment alone [10,11], thus indicating surgical intervention as suggested in highly selected patients with the goal of providing time off of systemic chemotherapy.

Our study thus aims to provide further insights in this complex and still unclear field of research.

OBJECTIVES

Primary Objective

Primary aim of the study is to compare the efficacy of liver resection vs. medical therapy alone in Breast Cancer Liver Metastasis (BCLM) patients.

Secondary Objectives

- To assess the recurrence rate after liver resection or medical treatment alone;
- To assess Recurrence free survival (RFS);
- To assess potential factors involved in both overall survival and RFS.

METHODS

Study design

Multicenter observational ambispective study.

Population

We will enroll all patients with BCLM underwent liver resection or medical treatment alone afferent to the Fondazione Policlinico Gemelli IRCSS of Rome (Italy), and other 8 International centers (as detailed in the attached document), following the inclusion and exclusion criteria hereafter detailed.

Study duration

The study will overall last 68 months since the approval of the present protocol by the sponsor center institutional review board (IRB), i.e. Fondazione Policlinico Gemelli IRCSS of Rome (Italy), and of all the satellite centers. The prospective enrolment of patients will last till the December 31, 2023 and follow-up phase will last for other 5 years, till December 31, 2028.

Study phases

The study foresees two distinct phases:

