To assess potential prognostic factors of 5-year RFS and OS, both univariable and multivariable Cox proportional hazards regression models will be fitted, and hazard ratios (HR) and 95% confidence intervals (CI) consequently reported. The proportionality of the hazards will be assessed by visual inspection of the hazards and Schoenfeld residuals. In case of doubtful proportionality, Cox weighted regression models will be fitted. “*survival*” and “*coxphw*” R packages will be used for the whole analysis [21-24]. The predictors to be included in the multivariable model will be selected on the basis of univariable analysis ($p < 0.05$ or suggestive, i.e. $0.05 \leq p < 0.10$) and expert opinion, also considering the possibility of overcoming the rule of 10 events per variable (EPV) [25,26]. Statistical significance will be set at a p-value < 0.05 . Suggestive p-values will be further reported ($0.05 \leq p < 0.10$). All analyses will be performed with R software version 4.2.0 (CRAN ®, R Core 2022) [27].

References

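### The only planned comparison of overall survival between surgery and medical therapy is an unadjusted log-rank test, and no adjusted treatment hazard ratio is named as the efficacy estimate of this non-randomised study

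*Protocol*

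**What the plan says.** - **Design.** The Protocol (Study design) describes a "Multicenter observational ambispective study". Treatment is not randomised. The background text ahead of the Objectives summarises earlier work as "thus indicating surgical intervention as suggested in highly selected patients with the goal of providing time off of systemic chemotherapy".
- **Primary question.** Primary endpoint: "The primary endpoint is to analyze the efficacy of liver surgery as compared to medical therapy alone in terms of 5-years overall survival".
- **Analysis of survival by group.** Statistical analysis: "Overall survival and RFS probabilities at 5 years will be estimated using the Kaplan Meier method and compared by the log-rank test". No stratification, matching or weighting is stated.
- **Sizing.** The sample size calculation rests on "a two-sided log-rank test with an overall sample size of 117 subjects".
- **Regression.** The Cox models have a different stated purpose: "To assess potential prognostic factors of 5-year RFS and OS, both univariable and multivariable Cox proportional hazards regression models will be fitted". That corresponds to a secondary endpoint, "To assess potential predictive factors of 5-years overall survival in patients with breast cancer". On covariates: "The predictors to be included in the multivariable model will be selected on the basis of univariable analysis", with a threshold of p < 0.10 and expert opinion added.

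**The concern.** The primary question is causal: does surgery work better than medical therapy alone? The groups are formed by clinical selection, and eligibility is wide (any treatment, extra-hepatic disease allowed), so nothing in the design makes them comparable. An unadjusted log-rank test then estimates the effect of surgery plus the effect of being the kind of patient who is offered surgery. It can show a benefit where none exists, or enlarge a real one, and a larger sample makes a false positive more likely.

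The Cox model could remove much of this for measured factors. However, it is assigned to another objective, does not name treatment as a fixed term, and fixes no confounder in advance. If the log-rank and the Cox model disagree, the protocol does not say which one answers the primary question. A significant log-rank could be reported as the efficacy result beside an adjusted hazard ratio near 1.

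**Working it through.** **1. The plan's own figure.** The planned hazard ratio follows from the two 5-year survival rates: ln(0.60)/ln(0.25) = 0.3685, stated as 0.37. With exponential survival, 30 years of uniform accrual, 5 years of follow-up, no drop-out and 117 patients split 15/85, the expected deaths are 96.47 and 14.28, matching the stated 96.5 and 14.3. Log-rank power by the Lakatos method at N = 117 is 88.6% with one-year intervals, 91.1% with half-year intervals and 93.3% with very fine ones. The stated 90% is consistent with these. The 117 is therefore an unadjusted two-group log-rank calculation with no allowance for confounding. The planning effect itself is based on a case-matched comparison (reference 10), whereas this study's own comparison is neither matched nor adjusted.

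**2. Inputs for the illustration.** From the protocol: 5-year survival of 25% on medical therapy, 15% surgical patients, about 500 patients in the retrospective phase and 675–720 overall (700 used). Assumed, because the documents give no figures: one binary adverse factor with the prevalences and hazard ratios below, exponential survival, and complete follow-up censored at 5 years.

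**3. One case by hand.** The adverse factor is present in 10% of surgical and 50% of medical patients, doubles the hazard, and surgery has no effect. Let S be 5-year survival without the factor, so that survival with it is S². In the medical group 0.5S + 0.5S² = 0.25, so S = (√3 − 1)/2 = 0.366 and S² = 0.134. Surgical survival is then 0.9 × 0.366 + 0.1 × 0.134 = 0.343. Selection alone gives an apparent 34% vs 25%. The simulated crude hazard ratio is about 0.76.

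**4. Log-rank rejection at two-sided 0.05 with no true effect** (10,000 simulated studies per scenario):

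| Adverse factor, surgical vs medical | Its hazard ratio | n = 500 | n = 700 |
|---|---|---|---|
| equal | – | 5.4% | 5.2% |
| 30% vs 40% | 1.5 | 6–8% (range over the three mild cases) | 5.4% |
| 40% vs 50% | 2 | as above | 7.7% |
| 30% vs 50% | 1.5 | as above | 9.4% |
| 20% vs 50% | 1.5 | 12% | 15% |
| 10% vs 50% | 2 | 41% | 55% |
| 10% vs 60% | 2 | 60% | 75% |

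A separate simulation using a favourable factor (hazard ratio 0.5, 70% of surgical vs 30% of medical patients) also gives about 55% at n = 700, with a crude hazard ratio of about 0.78.

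**5. Crude against adjusted, 10% vs 50% case** (4,000 studies each). With no true effect, the crude 95% interval contains 1 in 58% of studies at n = 500 and 45% at n = 700. A Cox model with treatment and the factor covers it in 95% and rejects in 5%. Among studies with a significant log-rank, the adjusted hazard ratio is also significant in only 5% (n = 500) and 4% (n = 700).

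**6. If the planned effect is real.** With a true hazard ratio of 0.37 and the same imbalance, the crude estimate is 0.29, with coverage of 80% at n = 500 and 74% at n = 700. The adjusted estimate is 0.37, with coverage of 94–95%.

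**7. Feasibility of adjustment.** At the planning rates, 700 patients yield 700 × (0.85 × 0.75 + 0.15 × 0.40) = 488 deaths by 5 years. Events needed for 90% power are (1.960 + 1.282)² / [0.15 × 0.85 × (ln 0.3685)² × (1 − R²)], where R² (assumed) measures how well the confounders predict treatment. This gives 83 at R² = 0, 104 at 0.2 and 166 at 0.5. With 488 deaths, the smallest benefit detectable at 90% power is a hazard ratio of 0.66 at R² = 0 and 0.56 at R² = 0.5.

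**The case against.** - **The planned Cox model already does much of this.** This largely stands. If treatment is a candidate predictor, a significant log-rank almost always means a univariable p below 0.10. In repeat simulations of five no-effect scenarios, treatment and the confounder both passed that screen in every study with a significant log-rank. The adjusted hazard ratio would then be fitted and reported. But the protocol does not list the candidates, so treatment's place in the model is a reasonable reading, not stated text. It also leaves open which result is the efficacy estimate.
- **The log-rank is never called primary.** True. The link is that it is the only survival comparison stated between the groups and the basis of the sample size.
- **The size rests on assumed imbalance.** True. Mild imbalance gives rejection close to nominal. The near-total disagreement in step 5 is specific to that case. Elsewhere, the share of significant log-ranks whose adjusted result is also significant was about 13–17% (20% vs 50%, hazard ratio 1.5), 39–44% (40% vs 50%, hazard ratio 2) and 55–69% (30% vs 40%, hazard ratio 1.5, from few significant studies).
- **Adjustment is no cure.** True. The 95% coverage assumes that the only confounder is measured perfectly. The variable list names neither performance status nor comorbidity, either of which could drive selection for surgery.
- **Details belong in a separate analysis plan.** This could cover the exact covariate list. It does not cover the main point, because the protocol has its own statistical analysis plan section that fixes the tests and the selection thresholds.

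**Conclusion.** The concern holds and must be fixed, because it affects the validity of the primary conclusion. The protocol poses an efficacy question in a selected, non-randomised population, answers it with an unadjusted test, and designates no adjusted treatment effect. The text establishes this without any simulation.

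The size of the bias cannot be known from the documents. It is negligible if the groups are nearly balanced and severe if they are not: across the assumed range, false-positive rates run from about 5% to 75% at 700 patients. If the planned effect is real, the conclusion that surgery helps survives, but in the case examined the crude estimate overstates the effect. All these figures assume one binary confounder, exponential survival and complete 5-year follow-up.

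**What to change.** In the Protocol's Statistical analysis section:

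- Name the adjusted hazard ratio for treatment, with its 95% confidence interval, from the already planned Cox model for overall survival as the primary efficacy estimate.
- Force treatment into that model.
- Fix the main confounders in advance on clinical grounds, not by univariable p-value. Use variables already collected and known at treatment start, such as extra-hepatic disease; number, size and distribution of metastases; receptor status; age; year of liver metastasis diagnosis; and centre.
- Keep the Kaplan-Meier curves and log-rank test as descriptive.
- State residual confounding as a limitation. Propensity-score weighting is optional as a sensitivity analysis.

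**Cost.** Protocol wording and a little more analysis, with no new data. The price is a somewhat wider interval. With one confounder (10% vs 50%, hazard ratio 2), the standard error of the log hazard ratio at n = 700 rises from 0.130 to 0.136 (about 5%). A fuller model was also simulated with no true effect: that confounder, six more binary factors (40% vs 50%, hazard ratio 1.2) and nine centres with surgical shares of 5–25% (600 studies each). The standard error rises from 0.133 to 0.145 at n = 700 (about 9%) and from 0.157 to 0.172 at n = 500 (about 10%), with about 510 and 365 deaths. In return, a crude hazard ratio of about 0.70 becomes 1.00–1.02, and rejection falls to about 5%.

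### The surgery-versus-medical log-rank test is not stratified by centre and centre is not a pre-specified Cox term, so differences between the nine centres may confound the comparison

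*Protocol*

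**What the plan says.** The Protocol describes a "Multicenter observational ambispective study" (Study design). Patients come from "Fondazione Policlinico Gemelli IRCSS of Rome (Italy), and other 8 International centers" (Population), so nine centres. The Sample size calculation expects, for the retrospective and "prospective phase 75-80 patients/center, for overall sample of 675-720 patients". The list under Variables and procedures includes "Name of the participating center".

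The comparison of resection with medical therapy is fixed under Statistical analysis: "Overall survival and RFS probabilities at 5 years will be estimated using the Kaplan Meier method and compared by the log-rank test". No stratum or adjustment is attached to that test, and the sample size rests on the same plain two-sided log-rank.

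The Cox models have a different stated purpose: "To assess potential prognostic factors of 5-year RFS and OS, both univariable and multivariable Cox proportional hazards regression models will be fitted". Their predictors are chosen by a univariable screen (p below 0.10, counting the suggestive band) and by expert opinion. Centre is neither named as a predictor nor excluded.

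**The concern.** Treatment is not randomised within or between centres. The protocol's background calls the role of resection controversial and describes surgery as suggested for highly selected patients, so different resection rates across nine international centres are plausible. Background survival may differ as well, through referral, drug access or follow-up practice.

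If both vary, an unstratified log-rank partly compares patients of high-resection centres with patients of low-resection centres. It also treats patients of one centre as independent. Two consequences are possible:

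- The false-positive rate of the primary comparison rises above 5%.
- If resected share and survival are related across centres, the hazard ratio (HR) itself is shifted.

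A model with tumour and patient features but no centre would leave unrecorded centre differences in place.

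**Working it through.** **Inputs from the Protocol.** 1 + 8 = 9 centres; 9 x 75 = 675 and 9 x 80 = 720 patients, matching the stated total. Resected share 0.15. Five-year OS 25% (medical) and 60% (surgery). Two-sided alpha 0.05.

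**The plan's own figures.**
- HR = ln(0.60)/ln(0.25) = 0.368, stated as 0.37.
- Control hazard = -ln(0.25)/5 = 0.277 per year.
- With uniform accrual over 30 years plus 5 years of follow-up, P(event) = 1 - [exp(-5h) - exp(-35h)]/(30h), where h is the hazard.
- Expected events: 117 x 0.85 x 0.970 = 96.5 and 117 x 0.15 x 0.814 = 14.3, both as stated.
- Power at 117 patients came out at 92.2-93.8% by the Lakatos method rather than 90%. Nothing here depends on that gap.

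**Assumptions not in the Protocol.** These are the spread of survival and of resected share between centres, and their correlation. To show what the spreads mean, at one SD either side of the centre average:
- Log-hazard SD 0.2: control five-year OS from 0.25^exp(0.2) = 18% to 0.25^exp(-0.2) = 32%.
- Log-hazard SD 0.4: 13% to 40%, by the same formula.
- Logit-share SD 0.7 around 15%: resected share from 8% to 26%. SD 1.0: 6% to 32%.

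**Test.** Unstratified: Z = U/sqrt(V), where U sums observed minus expected surgery deaths and V is its variance; reject if |Z| > 1.96; estimated HR = exp(U/V). Stratified: compute U and V within each centre and add them.

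**Simulation 1.** 9 x 75 patients, true HR 1, follow-up cut at 5 years, 1,000 studies per setting. The Monte Carlo standard error at 5% is sqrt(0.05 x 0.95/1000) = 0.7 points. Here a positive correlation means that centres resecting more have better survival.

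| SD log-hazard | SD logit share | Correlation | Unstratified error | Stratified error | Unstratified mean HR |
|---|---|---|---|---|---|
| 0 | 1.0 | 0 | 4.7% | 4.5% | 1.00 |
| 0.4 | 0 | 0 | 6.3% | 5.6% | 1.01 |
| 0.2 | 0.5 | 0 | 4.9% | 5.2% | 1.01 |
| 0.2 | 0.5 | 0.5 | 8.1% | 5.7% | 0.97 |
| 0.2 | 1.0 | 0 | 8.7% | 5.8% | 1.01 |
| 0.2 | 1.0 | 0.5 | 12.2% | 4.5% | 0.93 |
| 0.4 | 1.0 | 0 | 14.3% | 4.2% | 1.02 |
| 0.4 | 1.0 | 0.5 | 30.9% | 4.6% | 0.87 |

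Across all settings, the stratified mean HR stayed at about 1.00-1.01.

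**Simulation 2.** 9 x 78 patients, 2,000 studies per setting, log-hazard SD 0.2-0.4, several independent runs. With share and survival unrelated (share SD 0.7-1.0), the unstratified error was about 7-14%; one run reached 15.1%. With correlation -0.5 between share and log-hazard (the same direction as +0.5 in the table; share SD 0.8), it was about 9-24%, with a mean HR of about 0.95-0.89. The stratified test stayed at about 4-6%.

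**Cost in power.** At a true HR of 0.65, power was 87% stratified against 85% unstratified, and 90.9% against 88.4% in a second run. With three of the nine centres having no resections, the two tests were practically equal (83.0% and 82.5%).

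**The case against.** **The Cox models do not ignore centre.** A reader might infer that they do, or that centre enters only by chance. The text does not support this: centre is a recorded variable and may pass the univariable screen or be added by expert opinion. Put through the p < 0.10 screen on 8 degrees of freedom, centre was kept in 85% of simulated studies at log-hazard SD 0.2, in 98% at 0.3 and in at least 99.6% at 0.4. Stratifying only when it was kept held the error at 4.5-5.4%. This stands for the Cox models, provided that centre is offered as a candidate, which the protocol neither states nor rules out. It does not help the log-rank test, which has no selection step.

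**The harm is conditional.** The protocol gives no between-centre variation. If either resected share or survival does not vary, the plain test stays near 5%. The HR is biased only if the two are related, and the opposite sign would bias against surgery. All of this stands.

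**The bias is small against the design HR of 0.37.** True under the assumed spreads: centre alone would not produce an effect of that size. But at a 15% share the study would hold 0.15 x 675 = 101 to 0.15 x 720 = 108 resected patients, and power at HR 0.65 was already 85-91%. Much weaker effects than 0.37 can therefore reach significance.

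**Centre is one slice of a wider gap.** The log-rank adjusts for nothing, including extra-hepatic disease, lesion number, receptor status and calendar period. This also stands. The 4-6% for the stratified test holds because the simulations contain no patient-level confounding.

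**Conclusion.** The point holds in a limited form. The protocol fixes an unstratified log-rank as its comparison of surgery with medical therapy in a non-randomised nine-centre study, and does not pre-specify centre in the Cox models although it records it. This is a choice in the text, not a detail left open.

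The size depends on assumed spreads: log-hazard SD 0.2-0.4 and logit-share SD 0.7-1.0. Under these, the 5% test runs at about 7-14% if share and survival are unrelated, and at about 9-24% with a spurious HR of about 0.95-0.89 at correlation -0.5 (share SD 0.8). Smaller spreads do less harm, and no variation in survival does none.

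Two stronger conclusions are not supported. The documents do not show that centre differences do distort the surgery effect, or in which direction. Nor would a centre-stratified test become a valid 5% test of surgery, because patient-level confounding remains.

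**What to change.** In the Protocol, Statistical analysis:

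- Replace the plain log-rank by a log-rank stratified by participating centre, for both OS and RFS.
- In the Cox models that estimate the surgery effect, pre-specify centre as a stratum, or as a fixed factor if the weighted Cox fallback is used, whatever the univariable screen shows.
- Keep the unstratified result as a sensitivity analysis, and report the resected share per centre.

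Make the change before the interim analysis planned at the end of phase I, so that it counts as pre-specified. It takes a few sentences and no new data. A centre with only one treatment type adds nothing to the stratified contrast, which the table of resected shares will show; the simulations found no material loss of power, even with three such centres. Adjustment for patient-level factors must be planned in addition.
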